### QUALITY CONTROL

#### Data source quality control

When defining cohorts for indications, a systematic search of possible codes for inclusion will be identified using the *CodelistGenerator* R package (<https://github.com/darwin-eu/CodelistGenerator>). This package allows the user to define a search strategy and will use this to query the vocabulary tables of the OMOP common data model so as to find potentially relevant codes. In addition, the *CohortDiagnostics* (<https://github.com/OHDSI/CohortDiagnostics>) and *DrugExposureDiagnostics* (<https://cran.r-project.org/web/packages/DrugExposureDiagnostics/index.html>) R packages will be run, if needed, to assess the use of different codes across the data sources contributing to the study and identify any codes potentially omitted in error. The *DrugExposureDiagnostics* package evaluates ingredient-specific attributes and patterns in drug exposure records.

The study code will be based on DARWIN EU® R packages: *IncidencePrevalence* to estimate the prevalence of individuals with a recorded immunoglobulin prescription and *CohortCharacteristics* and *DrugUtilisation* to characterise the drug use and describe patient characteristics. These packages will include numerous automated unit tests to ensure the validity of the codes, alongside software peer review and user testing. The R package will be made publicly available via GitHub.

## **PLANS FOR DISSEMINATING AND COMMUNICATING STUDY RESULTS**

A PDF report including an executive summary, and the specified tables and/or figures will be submitted to EMA by the DARWIN EU® CC upon completion of the study.

An interactive dashboard incorporating all the results (tables and figures) will be provided alongside the PDF report. The full set of underlying aggregated data used in the dashboard will also be made available, if requested.

## ANNEX IV. Preliminary lists with concept definitions

List of conditions concepts definition is provided in the table below:

Table S2. Preliminary list of condition definitions.

Phenotype	Concept name	Concept id (including descendants)	Exclude concept id	Vocabulary
Haematology	Immune thrombocytopenia	4103532	No	SNOMED
Haematology	Acquired von Willebrand disease	4125641	No	SNOMED
Haematology	Neonatal alloimmune thrombocytopenia	4345345	No	SNOMED
Hepatology	Viral hepatitis, type A	4223947	No	SNOMED
Infectious diseases	Measles	4030555	No	SNOMED
Infectious diseases	Exposure to Measles virus	40479413	No	SNOMED
Internal medicine	Acute febrile mucocutaneous lymph node syndrome	314381	No	SNOMED
Internal medicine	Idiopathic inflammatory myopathy	45765443	No	SNOMED
Internal medicine	Dermatomyositis	80182	No	SNOMED
Internal medicine	Antineutrophil cytoplasmic antibody positive vasculitis	42535714	No	SNOMED
Internal medicine	Systemic lupus erythematosus	257628	No	SNOMED
Neurology	Guillain-Barre syndrome	4164770	No	SNOMED
Neurology	Chronic inflammatory demyelinating polyradiculoneuropathy	381009	No	SNOMED
Neurology	Motor neuropathy with multiple conduction block	4046338	No	SNOMED
Neurology	Myasthenia gravis	76685	No	SNOMED
Neurology	Stiff-person syndrome	379008	No	SNOMED
Neurology	Eaton-Lambert syndrome	4237155	No	SNOMED
Other indications*	Malignant melanoma of skin	141232	No	SNOMED
Other indications*	Malignant neoplastic disease	443392	No	SNOMED
Other indications*	Neoplasm of hematopoietic cell type	4189640	No	SNOMED
Other indications*	Malignant neoplasm of skin	4155297	Yes	SNOMED
Other indications*	Carcinoma in situ	433435	Yes	SNOMED
Other indications*	Paraneoplastic encephalitis	4312671	No	SNOMED
Other indications*	Autoimmune encephalitis	4318558	No	SNOMED
Other indications*	Epilepsy	380378	No	SNOMED
Other indications*	Seizure disorder	4029498	No	SNOMED
Other indications*	Progressive systemic sclerosis	40485046	No	SNOMED
Other indications*	Sjogren's syndrome	254443	No	SNOMED
Other indications*	COVID-19	37311061	No	SNOMED
Other indications*	Alzheimer's disease	378419	No	SNOMED

Phenotype	Concept name	Concept id (including descendants)	Exclude concept id	Vocabulary
Primary immunodeficiency syndrome	Primary immune deficiency disorder	4239314	No	SNOMED
Primary immunodeficiency syndrome	Congenital immunodeficiency disease	4263109	No	SNOMED
Primary immunodeficiency syndrome	Lymphocyte function antigen-1 defect	4098626	No	SNOMED
Primary immunodeficiency syndrome	Transient hypogammaglobulinemia of infancy	4230184	No	SNOMED
Secondary immunodeficiencies	Secondary immune deficiency disorder	4140977	No	SNOMED
Secondary immunodeficiencies	Adult-onset immunodeficiency	42536602	No	SNOMED
Transplantation	Solid organ transplant to recipient	4208341	No	SNOMED
Transplantation	Transplantation of bone marrow	4028623	No	SNOMED
Systemic infections	Sepsis caused by Gram negative bacteria	40493038	No	SNOMED
Systemic infections	Bacteraemia	132736	No	SNOMED
Bacterial infections	Bacterial infectious disease	432545	No	SNOMED
Central nervous system infections	Meningitis	435785	No	SNOMED
Fungal infections	Opportunistic mycosis	432248	No	SNOMED
Fungal infections	Invasive fungal infection	36717290	No	SNOMED
Gastrointestinal & intra-abdominal infections	Peritonitis	196152	No	SNOMED
Gastrointestinal & intra-abdominal infections	Gastrointestinal infection	37396146	No	SNOMED
Gastrointestinal & intra-abdominal infections	Acute diarrhea	4261727	No	SNOMED
Respiratory & ear, nose, throat, ocular infections	Sinusitis	4283893	No	SNOMED
Respiratory & ear, nose, throat, ocular infections	Respiratory tract infection	4170143	No	SNOMED
Respiratory & ear, nose, throat, ocular infections	Otitis	4183452	No	SNOMED
Respiratory & ear, nose, throat, ocular infections	Conjunctivitis	379019	No	SNOMED
Respiratory & ear, nose, throat, ocular infections	Bronchitis	256451	No	SNOMED
Urinary infections	Urinary tract infectious disease	81902	No	SNOMED
Viral infections	Herpesvirus infection	435463	No	SNOMED
Viral infections	Disease caused by Picornaviridae	4022207	No	SNOMED

\* = Prespecified indications of use classified as 'Other indications' will be assessed overall and separately for each indication, where available, as specified in [section 8.6.3](#).

List of medicines concepts definition is provided in the table below:

Table S3. Preliminary list of immunoglobulin and antibiotic ingredient definitions.

Substance Name	Concept name	Class	ATC code	Ingredient Concept ID	Include descendants
respiratory syncytial virus immune globulin intravenous	respiratory syncytial virus immune globulin intravenous	Immunoglobulins	J06B	19013765	Yes
immunoglobulin G	immunoglobulin G	Immunoglobulins	J06BA	19117912	Yes
freeze-dried pepsin-treated human normal immunoglobulin	freeze-dried pepsin-treated human normal immunoglobulin	Immunoglobulins	J06BA	35197905	Yes
ph4-treated acidic human normal immunoglobulin	ph4-treated acidic human normal immunoglobulin	Immunoglobulins	J06BA	35197913	Yes
ph4-treated acidic human normal immunoglobulin(for s.c. injection)	ph4-treated acidic human normal immunoglobulin(for s.c. injection)	Immunoglobulins	J06BA	35197969	Yes
polyethylene glycol-treated human normal immunoglobulin	polyethylene glycol-treated human normal immunoglobulin	Immunoglobulins	J06BA	35198039	Yes
freeze-dried ph4-treated human normal immunoglobulin	freeze-dried ph4-treated human normal immunoglobulin	Immunoglobulins	J06BA	35198103	Yes
freeze-dried sulfonated human normal immunoglobulin	freeze-dried sulfonated human normal immunoglobulin	Immunoglobulins	J06BA	35198193	Yes
freeze-dried polyethylene glycol-treated human normal immunoglobulin	freeze-dried polyethylene glycol-treated human normal immunoglobulin	Immunoglobulins	J06BA	35198206	Yes
immunoglobulin M, human	immunoglobulin M, human	Immunoglobulins	J06BA	42903696	Yes
immunoglobulin A	immunoglobulin A	Immunoglobulins	J06BA	43531966	Yes
Rho(D) immune globulin	Rho(D) immune globulin	Immunoglobulins	J06BB01	535714	Yes
tetanus immune globulin	tetanus immune globulin	Immunoglobulins	J06BB02	35604680	Yes
varicella-zoster immune globulin	varicella-zoster immune globulin	Immunoglobulins	J06BB03	543291	Yes
hepatitis B immune globulin	hepatitis B immune globulin	Immunoglobulins	J06BB04	501343	Yes
rabies immune globulin, human	rabies immune globulin, human	Immunoglobulins	J06BB05	19135830	Yes
Immunoglobulin Anti-Rubella	Immunoglobulin Anti-Rubella	Immunoglobulins	J06BB06	40798902	Yes
human vaccinia immune globulin	human vaccinia immune globulin	Immunoglobulins	J06BB07	19122168	Yes

Substance Name	Concept name	Class	ATC code	Ingredient Concept ID	Include descendants
staphylococcus epidermidis immunoserum rabbit	staphylococcus epidermidis immunoserum rabbit	Immunoglobulins	J06BB08	43013161	Yes
staphylococcus aureus immunoserum	staphylococcus aureus immunoserum	Immunoglobulins	J06BB08	43532492	Yes
cytomegalovirus immune globulin	cytomegalovirus immune globulin	Immunoglobulins	J06BB09	586491	Yes
diphtheria antitoxin	diphtheria antitoxin	Immunoglobulins	J06BB10	19031041	Yes
Hepatitis A immunoglobulin	hepatitis A immunoglobulin; systemic	Immunoglobulins	J06BB11	21601269	Yes
Immunoglobulin Anti-Tickborne Encephalitis	Immunoglobulin Anti-Tickborne Encephalitis	Immunoglobulins	J06BB12	40798903	Yes
pertussis immunoglobulin	pertussis immunoglobulin; systemic	Immunoglobulins	J06BB13	21601271	Yes
measles immunoglobulin	measles immunoglobulin; systemic	Immunoglobulins	J06BB14	21601272	Yes
Mumps immunoglobulin	mumps immunoglobulin; systemic	Immunoglobulins	J06BB15	21601273	Yes
anthrax immune globulin	anthrax immune globulin	Immunoglobulins	J06BB19	35605786	Yes
Bacillus anthracis immunoserum rabbit	Bacillus anthracis immunoserum rabbit	Immunoglobulins	J06BB19	42903978	Yes
Nebacumab	Nebacumab	Immunoglobulins	J06BC01	40798985	Yes
raxibacumab	raxibacumab	Immunoglobulins	J06BC02	43013193	Yes
bezlotoxumab	bezlotoxumab	Immunoglobulins	J06BC03	1718211	Yes
obiltoxaximab	obiltoxaximab	Immunoglobulins	J06BC04	35603994	Yes
palivizumab	palivizumab	Immunoglobulins	J06BD01	537647	Yes
MOTAVIZUMAB	MOTAVIZUMAB	Immunoglobulins	J06BD02	36851985	Yes
tixagevimab	tixagevimab	Immunoglobulins	J06BD03	702418	Yes
ansuvimab	ansuvimab	Immunoglobulins	J06BD04	739418	Yes
sotrovimab	sotrovimab	Immunoglobulins	J06BD05	1536976	Yes
REGDANVIMAB	REGDANVIMAB	Immunoglobulins	J06BD06	36858135	Yes
casirivimab	casirivimab	Immunoglobulins	J06BD07	37003288	Yes

Substance Name	Concept name	Class	ATC code	Ingredient Concept ID	Include descendants
nirsevimab	nirsevimab	Immunoglobulins	J06BD08	746155	Yes
Sipavibart	Sipavibart	Immunoglobulins	J06BD09	1253346	Yes
Tetracyclines	Tetracyclines	Antibiotics	J01A	21602797	Yes
Amphenicols	Amphenicols	Antibiotics	J01B	21602813	Yes
Beta-lactam antibacterials, penicillins	Beta-lactam antibacterials, penicillins	Antibiotics	J01C	21602818	Yes
Other beta-lactam antibacterials	Other beta-lactam antibacterials	Antibiotics	J01D	21602868	Yes
Sulfonamides and trimethoprim	Sulfonamides and trimethoprim	Antibiotics	J01E	21602929	Yes
Macrolides, lincosamides and streptogramins	Macrolides, lincosamides and streptogramins	Antibiotics	J01F	21602968	Yes
Aminoglycoside antibacterials	Aminoglycoside antibacterials	Antibiotics	J01G	21602990	Yes
Quinolone antibacterials	Quinolone antibacterials	Antibiotics	J01M	21603006	Yes
Other antibacterials	Other antibacterials	Antibiotics	J01X	21603041	Yes

List of immunoglobulins brands concepts definition is provided in the table below:

Table S4. Preliminary list of immunoglobulin brand definitions.

Brand Name	Concept name	Concept ID	Include descendants
Flebogamma DIF	Immunoglobulin G Injectable Solution [Flebogamma DIF]	35745366	Yes
Flebogamma DIF	Immunoglobulin G Injection [Flebogamma DIF]	21085351	Yes
Flebogamma DIF	Immunoglobulin G Prefilled Syringe [Flebogamma DIF]	36893531	Yes
Kiovig	Immunoglobulin G Injectable Solution [Kiovig]	41018997	Yes
Kiovig	Immunoglobulin G Prefilled Syringe [Kiovig]	36887597	Yes
Kiovig	Immunoglobulin G Injection [Kiovig]	21124428	Yes
Privigen	immunoglobulin G Injection [Privigen]	40220571	Yes
Privigen	Immunoglobulin G Injectable Solution [Privigen]	40726095	Yes
Privigen	Immunoglobulin G Intravenous Solution [Privigen]	36783517	Yes
Privigen	Immunoglobulin G Prefilled Syringe [Privigen]	36886637	Yes
Octagam (5% and 10%)	immunoglobulin G Injection [Octagam]	40220559	Yes
Octagam (5% and 10%)	Immunoglobulin G Injectable Solution [Octagam]	40726091	Yes
Octagam (5% and 10%)	Immunoglobulin G Prefilled Syringe [Octagam]	36889584	Yes

Brand Name	Concept name	Concept ID	Include descendants
Octagam (5% and 10%)	Immunoglobulin G Intravenous Solution [Octagam]	36783515	Yes
Yimmugo	immunoglobulin G Injection [Yimmugo]	1465644	Yes
Yimmugo	immunoglobulin G Injectable Solution [Yimmugo]	845238	Yes
Ig vena	Immunoglobulin G Injectable Solution [Ig Vena]	43659776	Yes
Intratect	Immunoglobulin G Injectable Solution [Intratect]	43785444	Yes
Intratect	Immunoglobulin G Prefilled Syringe [Intratect]	35757897	Yes
Intratect	Immunoglobulin G Injection [Intratect]	21134327	Yes
Iqymune	Immunoglobulin G Injection [Iqymune]	40726086	Yes
Iqymune	Immunoglobulin G Injectable Solution [Iqymune]	41018998	Yes
Panzyga/Globiga	immunoglobulin G Injection [Panzyga]	35201515	Yes
Panzyga/Globiga	Immunoglobulin G Injectable Solution [Panzyga]	36813729	Yes
Panzyga/Globiga	Immunoglobulin G Prefilled Syringe [Panzyga]	35412031	Yes
Panzyga/Globiga	Immunoglobulin G Injectable Solution [Panzyga]	40726088	Yes
Gamunex	immunoglobulin G Injection [Gamunex]	40220604	Yes
Gamunex	Immunoglobulin G Injectable Solution [Gamunex]	40726093	Yes
Gamunex	Immunoglobulin G Intravenous Solution [Gamunex]	36783516	Yes
Gamunex	Immunoglobulin G Prefilled Syringe [Gamunex]	35762066	Yes
Hizentra	Immunoglobulin G Injectable Solution [Hizentra]	40726090	Yes
Hizentra	immunoglobulin G Injection [Hizentra]	40220468	Yes
Hizentra	immunoglobulin G Prefilled Syringe [Hizentra]	37498237	Yes
Hizentra	ph4-treated acidic human normal immunoglobulin(for s.c.injection) Injectable Solution [Hizentra]	35152334	Yes
Hyqvia	Immunoglobulin G Injection [HyQvia]	35407336	Yes
Hyqvia	Immunoglobulin G Injectable Solution [HyQvia]	40988033	Yes
Hyqvia	Immunoglobulin G Prefilled Syringe [HyQvia]	35411221	Yes
Cuvitru	immunoglobulin G Injection [Cuvitru]	1718181	Yes
Cuvitru	Immunoglobulin G Injectable Solution [Cuvitru]	40726096	Yes
Cutaquig	immunoglobulin G Injection [Cutaquig]	789805	Yes
Cutaquig	immunoglobulin G Injectable Solution [Cutaquig]	36929633	Yes
Xembify	immunoglobulin G Injection [Xembify]	1361585	Yes
Xembify	immunoglobulin G Injectable Solution [Xembify]	845239	Yes
Gammagard	Immunoglobulin G Injectable Suspension [Gammagard]	41207103	Yes
Gammagard	immunoglobulin G Injection [Gammagard]	40220624	Yes
Gammagard	Immunoglobulin G Prefilled Syringe [Gammagard]	36891553	Yes
Gammagard	Immunoglobulin G Injectable Solution [Gammagard]	35749536	Yes
Gammagard	Immunoglobulin G Injectable Solution [Gammagard]	40726094	Yes

Brand Name	Concept name	Concept ID	Include descendants
Clairyg	Immunoglobulin G Injection [CLAIRYG]	35408919	Yes
Clairyg	Immunoglobulin G Injectable Solution [CLAIRYG]	43034816	Yes
Clairyg	Immunoglobulin G Prefilled Syringe [CLAIRYG]	43149994	Yes
Tegeline	Immunoglobulin G Injectable Solution [TEGELINE]	43034817	Yes
Tegeline	Immunoglobulin G Injection [TEGELINE]	35406781	Yes
Tegeline	Immunoglobulin G Prefilled Syringe [TEGELINE]	43172126	Yes
Pentaglobin	Immunoglobulin G Injectable Solution [Pentaglobin]	40721840	Yes
Pentaglobin	Immunoglobulin G Oral Solution [Pentaglobin]	43694274	Yes
Pentaglobin	human immunoglobulin Injectable Solution [Pentaglobin]	41207106	Yes
Pentaglobin	immunoglobulin M, human Injectable Solution [Pentaglobin]	42929914	Yes
Gammaplex	immunoglobulin G Injection [Gammaplex]	40220565	Yes
Gammaplex	Immunoglobulin G Injectable Solution [Gammaplex]	40726089	Yes
Nanogam/Optiglobin	Immunoglobulin G Injection [Nanogam]	36269625	Yes
Nanogam/Optiglobin	Immunoglobulin G Injectable Solution [Nanogam]	783868	Yes
Beriglobin	Immunoglobulin G Injectable Solution [Beriglobin]	43713448	Yes
Beriglobin	Immunoglobulin G Prefilled Syringe [Beriglobin]	41050285	Yes
Rhesonativ	Immunoglobulin G Injectable Solution [Rhesonativ]	40894536	Yes
Rhesonativ	Rho(D) Immune Globulin Injectable Solution [Rhesonativ]	43692085	Yes
Rhophylac	Immunoglobulin G Prefilled Syringe [Rhophylac]	41112997	Yes
Rhophylac	Rho(D) Immune Globulin Injectable Solution [Rhophylac]	35774715	Yes
Rhophylac	Rho(D) immune globulin Prefilled Syringe [Rhophylac]	40241802	Yes
Rhophylac	Rho(D) Immune Globulin Injection [Rhophylac]	43258523	Yes
Rhophylac	Rho(D) Immune Globulin Injectable Solution [Rhophylac 300]	43781959	Yes
Rhophylac	Rho(D) Immune Globulin Injectable Solution [Rhophylac 200]	43817962	Yes

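### Table S2 lists melanoma of skin as included in Oncology but excludes malignant neoplasm of skin with its descendants, so the list resolved as written drops melanoma

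*Protocol*

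**What the plan says.** Section 8.6.3 of the Protocol names Oncology as one of seven conditions in the residual group of proxy indications for objective 4. The group is to be reported as a whole and condition by condition, and the footnote to mock Table 5 in Section 8.8.4 repeats this. Table S2 in Annex IV does not print the word Oncology; the cancer concepts appear there under the residual group's label. Four rows matter here, above all the one that excludes "Malignant neoplasm of skin":

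- "Malignant melanoma of skin 141232 No SNOMED"
- "Malignant neoplastic disease 443392 No SNOMED"
- "Malignant neoplasm of skin 4155297 Yes SNOMED"
- "Carcinoma in situ 433435 Yes SNOMED"

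The No or Yes is the entry in the exclusion column. A fifth row, for neoplasms of haematopoietic cell type (4189640), is also included. The only id column begins "Concept id (including descendants", and no row is exempted from that rule. The Protocol gives no order in which inclusions and exclusions are applied, and no step that restores a concept after exclusion. Table S2 is titled as preliminary, and Section 8.6.3 says the covariate concept sets become final after EMA input.

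**The concern.** A malignant melanoma of skin is, by its name, a malignant neoplasm of skin. It is also a malignant neoplastic disease, so 443392 with descendants already brings it in. The separate melanoma row is therefore needed only to protect melanoma from an exclusion that would otherwise remove it. As the table stands, the exclusion carries its descendants and the inclusion has no stated priority, so that protection is not delivered.

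At stake is the Oncology result under objective 4, by brand, data source and each of the three indication windows. Section 9 says the true indication is not recorded directly and that diagnosis codes stand in for it, so nothing else in the data would supply an indication that the code list removes.

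**Working it through.** The Protocol states no figure on this point, so the check is one of set logic. D(x) denotes concept x with all its descendants.

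**Inputs from Table S2**
- Included: D(141232), D(443392), D(4189640).
- Excluded: D(4155297), D(433435).

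**Assumption.** The SNOMED hierarchy is not in the Protocol. From the concept names I take 141232 to lie under 4155297, and 4155297 under 443392. The rows for haematopoietic neoplasm and carcinoma in situ do not, by name, concern malignant melanoma and are set aside.

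**Is the melanoma row needed for inclusion?** Under the assumption, D(141232) lies within D(443392). The row adds nothing to the included set.

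**Three ways to combine the rows**, traced with melanoma, one other skin cancer (basal cell) and one non-skin cancer (lung) as examples:

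| Reading | Rule | Melanoma | Other skin cancer | Lung cancer |
|---|---|---|---|---|
| A | [D(141232) ∪ D(443392)] minus D(4155297) | out | out | in |
| B | [D(141232) ∪ D(443392)] minus the single concept 4155297 | in | in | in |
| C | [D(443392) minus D(4155297)] ∪ D(141232) | in | out | in |

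**Against the text**
- A follows the column header for every row. It makes the melanoma row redundant.
- B contradicts the header and defeats the exclusion, since the other skin cancers stay in.
- C gives both the melanoma row and the skin exclusion a purpose, but the Protocol states no such order.

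The literal reading (A) and the only reading in which every row does something (C) disagree on melanoma.

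**Who is affected under A**
- *Oncology result:* an initiator is lost if cutaneous melanoma is the only qualifying cancer code in the window. Any other included cancer code in that window keeps the patient in. The relative shortfall is (initiators with melanoma as the only qualifying code) ÷ (all initiators positive for Oncology under reading C). Neither count is in the Protocol.
- *Residual group overall:* the same patient is lost only if none of the other six conditions is coded in the window (encephalitis, epilepsy, systemic sclerosis, Sjögren syndrome, COVID-19, Alzheimer's disease). The number lost here cannot exceed the number lost from the Oncology result.

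**The case against.** The best counter-argument is that the table does not prove melanoma will be lost. The parent-child link is inferred from names, no resolution rule is written down, and melanoma survives under readings B and C. The list is also provisional. Annex III plans a systematic code search when indication cohorts are defined, with diagnostics run where needed to find codes left out by mistake. The study is descriptive, Section 9 already warns that proxy indications may be incomplete, and counts below 5 are suppressed, so a difference confined to melanoma may not show in many brand-by-source cells.

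Much of this stands, and it limits the claim. Four stronger readings are tempting and should not be drawn:

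- *All patients with melanoma disappear.* Only those with no other included cancer code in the window do.
- *The overall figure for the residual group loses all of those patients too.* It keeps any who have another listed condition.
- *The loss would pass unnoticed.* The planned code review could catch it, although the diagnostics are conditional.
- *The undercount can be given as a percentage.* The Protocol has no melanoma or Oncology counts, so any range would be a guess.

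The objection does not make the table coherent. Reading B conflicts with the header, and reading C is written nowhere. Preliminary status makes the correction cheap but leaves the contradiction in place. Section 5 dates the final protocol 19 January 2026 and the draft report 30 January 2026, eleven days later (30 − 19 = 11), so there is little time for a later review to find it.

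**Conclusion.** The inconsistency is real. Resolved as written, Table S2 removes melanoma of skin from Oncology and leaves its inclusion row without effect, while that row makes sense only if melanoma was meant to be kept. This rests on two assumptions: that the vocabulary places 141232 under 4155297, as the names indicate, and that the list is resolved as included minus excluded.

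The effect is confined to the Oncology result and, to no greater degree, the overall residual-group figure in objective 4. Its size cannot be derived from the documents. I judge it probably small, because the affected group is narrow: brand initiators with a cutaneous melanoma code and no other qualifying cancer code in the window. It should be corrected before the code is run, but no main estimate depends on it.

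**What to change.** Make one of two edits to Table S2:

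1. Replace the exclusion of 4155297 with an exclusion limited to skin malignancies other than melanoma; or
2. Keep the exclusion and state the order: apply the exclusions first, then add back 141232 with its descendants.

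If melanoma is in fact meant to be left out, delete its inclusion row and say so. In every case, label the cancer rows as Oncology so that the set can be traced to Section 8.6.3. Before execution, check whether 141232 is in the resolved code list: it should be present under either numbered edit. That check also settles the hierarchy assumption.

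The cost is one edit to a list that is still preliminary, plus one look at the resolved codes. Nothing in objectives 1 to 3 changes.

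### Two anti-D brand concepts carry an immunoglobulin G label, so objective 1 would count their records as immunoglobulin G rather than Rho(D)

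*Protocol*

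**What the plan says.** Section 8.6.1 defines the objective 1 exposure at ingredient level. Section 8.8.3 reports objective 1 prevalence by ingredient and route, stratified by sex and age. The ingredients are in Annex IV, Table S3. There, immunoglobulin G (J06BA, 19117912) and Rho(D) immune globulin (J06BB01, 535714) are separate entries, each taken with descendants.

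Table S4 holds the brand concepts used for objectives 2 to 4. Both anti-D brands appear there under two ingredients:

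- Rhesonativ: "Immunoglobulin G Injectable Solution [Rhesonativ" (40894536) and "Rho(D) Immune Globulin Injectable Solution [Rhesonativ" (43692085).
- Rhophylac: "Immunoglobulin G Prefilled Syringe [Rhophylac" (41112997), and five Rho(D) concepts such as "Rho(D) immune globulin Prefilled Syringe [Rhophylac" (40241802).

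Two other brands also span ingredient labels. Pentaglobin has "Immunoglobulin G Injectable Solution [Pentaglobin", "human immunoglobulin Injectable Solution [Pentaglobin" and "immunoglobulin M, human Injectable Solution [Pentaglobin". Hizentra has three immunoglobulin G rows and one row reading "ph4-treated acidic human normal immunoglobulin(for s.c.injection) Injectable Solution [Hizentra".

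For objective 3, Section 8.8.3 gives initial and cumulative dose per brand. Cumulative dose is built from defined daily doses and days exposed, and the Table 3 shell in Section 8.8.4 shows no unit. Section 8.6.1 calls the concept sets preliminary and leaves the final sets to later refinement with input from EMA.

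**The concern.** The plan treats Rho(D) and immunoglobulin G as different types, and type is the main stratifier of objective 1. Table S4 shows that the vocabulary holds records of one anti-D brand under either ingredient. A rule that collects every descendant of immunoglobulin G would then sort the same product into one type or the other according to the local mapping alone.

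The three sources start from different drug coding systems (Annex I): local codes mapped to UCD and ATC in Bordeaux, PZN in Germany, and Gemscript and dm+d in CPRD GOLD. A difference between sources in immunoglobulin G or Rho(D) prevalence could therefore be a mapping artefact. The planned figures cross ingredient with route, sex and age group, so an error in type would carry into each of them.

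A second, smaller question is which ingredient the objective 3 dose refers to when one brand row covers records under more than one ingredient.

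**Working it through.** The plan has no figure to reproduce on this point. The check counts the code lists and follows them through the objectives.

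**1. Ingredient labels per brand (Table S4).** The table has 72 rows with 72 distinct concept IDs, covering 24 brands. Four brands carry more than one ingredient label:

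| Brand | Rows by ingredient label |
|---|---|
| Rhesonativ | 1 immunoglobulin G, 1 Rho(D) |
| Rhophylac | 1 immunoglobulin G, 5 Rho(D) |
| Pentaglobin | 2 immunoglobulin G, 1 human immunoglobulin, 1 immunoglobulin M |
| Hizentra | 3 immunoglobulin G, 1 pH4-treated (subcutaneous) |

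The other 24 − 4 = 20 brands are immunoglobulin G only. The two anti-D brands have 2 + 6 = 8 rows, of which 1 + 1 = 2 are labelled immunoglobulin G and 1 + 5 = 6 Rho(D).

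**2. Route into objective 1.** Objective 1 uses Table S3, not Table S4. A record under 40894536 or 41112997 enters the immunoglobulin G set if that concept descends from 19117912. The names imply this, but the vocabulary is not part of the protocol, so it is an assumption. On that assumption, and with no exclusion in Table S3, the record counts as immunoglobulin G and not as Rho(D).

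**3. What moves and what does not.** Let G be the users of immunoglobulin G products and D the users of the two anti-D brands. For simplicity assume no overlap between them. Let f be the share of D recorded only under the two immunoglobulin G-labelled concepts, the rest being recorded only under Rho(D) concepts.

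- Counted as immunoglobulin G: G + fD
- Counted as Rho(D), from these brands: (1 − f)D
- Sum: G + fD + (1 − f)D = G + D, whatever f is

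Overall prevalence is unchanged because both ingredients are in Table S3. With f = 0 there is no error. With f = 1 every user of these two brands is counted under the wrong type. The protocol gives none of f, D or G, so the shift cannot be sized.

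**4. Dose (objective 3).** The brand-level summary would place records under different ingredient labels in one row. The protocol states no strength, unit or defined daily dose for any of these concepts, and no rule for which ingredient's dose applies. Whether the bases differ cannot be determined from it.

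**5. Pentaglobin and objective 2.** Table S3 has no ingredient named exactly human immunoglobulin, so the ancestry of 41207106 is not visible. Section 8.3 defines the objective 2 population by a record of a prespecified brand, which would include such a user. The abstract and Section 8.8.3 refer to immunoglobulin users more generally.

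**The case against.** The strongest reply has three parts.

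First, listing every concept that bears a brand name is the right way to capture a brand, and deleting rows from Table S4 would not change objective 1. This stands. The cause is source mapping together with the inclusion of all descendants in Table S3; Table S4 only makes the problem visible.

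Second, at most the records under two of the eight anti-D concepts are affected, and there may be none in any source. This stands too. A reader might infer that anti-D users as a whole are counted as immunoglobulin G users, that immunoglobulin G prevalence is inflated by some stated factor, or that the excess falls in particular sex or age strata. The protocol gives neither the mapping share nor the ratio of anti-D to immunoglobulin G users, so any such factor would be a product of guesses. It says nothing about who receives anti-D.

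Third, the lists are preliminary, and Section 8.6.1 promises review of code lists and phenotypes. This lowers the weight of the point but does not close it. No stated check requires one type per product. Annex III runs the drug exposure diagnostics only if needed. Table S2 has an exclusion column, while Tables S3 and S4 have none. Section 5 places the final protocol on 19 January 2026, execution in January and the draft report on 30 January. Sites return aggregates only, so a wrong type cannot be corrected centrally without a rerun.

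**Conclusion.** The point holds in a limited form. As written, and assuming the two concepts descend from 19117912, records under 40894536 and 41112997 would be reported as immunoglobulin G rather than Rho(D) in objective 1. Prevalence by type would then depend on source mapping. The affected share of the two brands' records is unknown, from 0 to 100%. Overall immunoglobulin prevalence is not affected, and brand capture in Table S4 is not at fault.

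Two further inferences go beyond the documents. A reader might conclude that brand doses pool different dose bases; the protocol leaves that risk open but does not show it. A reader might also conclude that some Pentaglobin users fall in the objective 2 numerator but outside its denominator. That is not established, because Section 8.3 defines the population by brand and the ancestry of 41207106 cannot be read from the protocol. Both call for a check when the lists are finalised.

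**What to change.** 1. In Table S3, for objective 1, exclude 40894536 and 41112997 with descendants from the immunoglobulin G set and add them to the Rho(D) set. Both steps are needed: exclusion alone would drop these records from the immunoglobulin total.
2. Keep all rows of Table S4, so that brand capture for objectives 2 to 4 is unchanged.
3. For Rhesonativ, Rhophylac, Pentaglobin and Hizentra, report the objective 3 dose separately by recorded ingredient and unit, unless the bases are confirmed to be the same.
4. When finalising the lists, confirm that 41207106 falls within the objective 2 user population.

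The cost is a small code-list edit before execution and a few more dose rows, some of which may fall below the minimum cell count of 5. No new data are needed.
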